8.4.2 UNANTICIPATED PROBLEMS REPORTING

1. Unanticipated problems (UPs) involving risks to participants or others

Events (internal or external, deaths, life-threatening experiences, injuries, or other) occurring during the research study, which in the opinion of the Monitoring Entity or the PD meet all of the following criteria:

a) Unexpected

in terms of nature, severity, or frequency, given (a) the research procedures described in the protocol-related documents, and (b) the characteristics of the subject population being studied;

AND

b) **Related to participation in the research** or there is a reasonable possibility or likelihood that the incident, experience, or outcome may have been caused by the procedures involved in the research;

AND

c) Harmful

the research places participants or others at a greater risk of harm (including physical, psychological, economic, or social harm) than was previously known or recognized.

- 2. **New Information** that indicates a change to the risks or potential benefits of the research in terms of severity or frequency or impacts the participant's willingness to participate (e.g., DSMB/DSMC Report, other safety information or publication, suspension or premature termination by the sponsor or investigator).
- 3. **Noncompliance:** An action or activity in human subject research at variance with the approved IRB protocol, other requirements and determinations of the IRB, the HRPP Policy Manual and other applicable policies of Stanford University, SHC, LPCH, VAPAHCS (e.g., VHA Handbook 1200.5), Palo Alto Veterans Institute for Research (PAVIR) or relevant state or federal laws.

When the event is:

- Possibly serious
 - Noncompliance that affects the rights or welfare of human subject research participants.
- Possibly continuous
 - A pattern of noncompliance that continues to occur after a report of noncompliance and a corrective action plan has been reviewed and approved by the IRB, after an investigator has been warned to correct errors or noncompliance, or a circumstance in which an investigator fails to cooperate with investigating or correcting non-compliance.
- 4. **Complaint** unresolved by the research team.
- 5. **Incarceration** when in the opinion of the PD it is in the best interest of the participant to remain in the study.

8.4.3 REPORTING UNANTICIPATED PROBLEMS TO PARTICIPANTS

N/A

9 STATISTICAL CONSIDERATIONS

9.1 STATISTICAL HYPOTHESES

- 1. Hypothesis 1: enroll 70 participants and retain ≥85% at 11 weeks.
- 2. Hypothesis 2: At least 60% of participants show an increase in emotional regulation as indicated by any one of the three: i) an increase in mPFC activation, ii) an increase in mPFC-amygdala connectivity, or iii) a decrease in amygdala activation relative to baseline, supporting that the targets can be modified in a majority of participants.

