
Objectives:

1. Demonstrate feasibility and 2. target engagement in a single arm clinical trial (Study 1). We will enroll 70 adults with elevated depressive symptoms (BDI \geq 14) who are also experiencing clinically meaningful insomnia (\geq 15 ISI). Given the high comorbidity rates, anxiety will not be exclusionary. Participants will receive six sessions of CBT-I over eight weeks. CBT-I is an efficacious intervention that improves subjective and objective measures of insomnia. At both baseline and post-treatment, we will assay emotion regulation neural targets (using fMRI), depressive symptoms and suicidality, and each subject will complete an over-night sleep EEG recording. Depression, suicidality, and insomnia symptoms (actigraphy and ISI) will be assayed at baseline and each week throughout treatment to assess week-to-week improvements following an increasing number of CBT-I sessions. Milestones (Go/NoGo Criteria): 1. Feasibility: Enroll 70 participants and retain ≥80% at the end of treatment; 2. Target Engagement: For a go decision at least 1 of 3 emotion regulation tasks must exhibit an improved group mean (M) value with a boundary value (Standard Deviation (SD)/2) in the direction of improvement for **both** amygdala reactivity ((M-SD/2) ≤-0.35) and amygdala-mPFC connectivity ((M+SD/2) ≥0.35. The targets that meet these criteria will be carried over as primary targets of emotion regulation network function in the R33 phase.

Endpoints: Primary Endpoint: emotion regulation brain function

Study Population: 70 patients with moderate to severe sleep disturbance and at least mild depressive symptoms as measured by the Beck Depression Inventory (BDI).

Phase or Stage: 1

Sites/Facilities Enrolling

sites/ Facilities Elli Olli

Participants:

Description of

Description of Study SL

Intervention/Experimental

Manipulation:

SLEEP MANIPULATION

The sleep manipulation is Cognitive Behavioral Therapy for Insomnia (CBT-I). Treatments will be delivered in six 50-minute treatment sessions within an eight-week period by a PhD psychologist who is experienced in administering the study treatments. The CBT-I therapy will be delivered according to protocols and materials from our large-scale VA implementation of CBT-I. These materials include a published sleep self-help book, a published therapist

The study will be conducted at Stanford University School of Medicine.

guide, and the CBT-I therapist manual.

[figure not shown]
Study Duration: 24 months

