OBJECTIVE: 1. Demonstrate feasibility and 2. target engagement in a single arm clinical trial (Study 1). We will enroll 70 adults with elevated depressive symptoms (BDI ≥ 14) who are also experiencing clinically meaningful insomnia (≥15 ISI) and at least mild depressive symptoms as measured by the Beck Depression Inventory (BDI). Participants will receive six sessions of Cognitive Behavioral Therapy for Insomnia (CBT-I) over eight weeks. CBT-I is an efficacious intervention that improves sleep patterns through a combination of sleep restriction, stimulus control, cognitive therapy targeting dysfunctional beliefs about sleep, and sleep hygiene education. At both baseline and post-treatment, we will assay emotion regulation neural targets (using functional magnetic resonance imaging), emotional distress, and each subject will complete an over-night sleep EEG recording. Depression, suicidality, and insomnia symptoms (actigraphy and ISI) will be assayed at baseline and each week throughout treatment to assess week-to-week improvements following an increasing number of CBT-I sessions. Milestones (Go/No-Go Criteria): Feasibility: Enroll 70 participants and retain ≥80% at the end of treatment; Target Engagement: For a go decision at least 1 of 3 emotion regulation tasks must exhibit an improved group mean (M) value with a boundary value (Standard Deviation (SD)/2) in the direction of improvement for both amygdala reactivity ((M-SD/2) \leq -0.35) and amygdala-mPFC connectivity ((M+SD/2) \geq 0.35. The targets that meet these criteria will be carried over as primary targets of emotion regulation network function in the R33 phase. NOVELTY & IMPACT: Characterizing these associations may offer the potential to gain a deeper understanding of the neurobiological mechanisms underlying depression in the presence of unhealthy sleep patterns. Our results will advance an evidence-based mechanistic approach to treating, and ultimately preventing, the emotionally distressing and potentially life-threatening impact of sleep disruption.

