3 OBJECTIVES AND ENDPOINTS

3.1 PRIMARY OBJECTIVES

3.1.1 GO/NO-GO MILESTONES

- 1. Feasibility of recruitment and retention: enroll 70 participants and retain ≥80% at 11 weeks. In our study of older adults (mean age=68.51, SD=5.78) described above, 87% of our sample was retained at the end of treatment visit at 11 weeks. In a prior study that included adults with comorbid depression and insomnia (mean age=47.4, SD=12.6), 93% of the individuals completed treatment⁸¹.
- 2. Emotion Regulation Network Target Engagement: This will be determined using the precision interval approach. The goal is to demonstrate sufficient variation for further investigation 82,83 . We hypothesize that CBT-I will improve ERN function by reducing amygdala reactivity and increasing amygdala-mPFC connectivity. Thus, for the amygdala, improvement is likely reflected in an absolute negative mean change value with a lower fixed-width interval boundary (M-SD/2), where M is the mean and SD is the standard deviation, which is also substantially in the negative direction. Similarly, the amygdala-mPFC improvement is reflected by an absolute increase mean change with an upper fixed-width interval boundary (M+SD/2). For a GO decision, we will require at least 1 of 3 emotion regulation neuroimaging tasks must exhibit improvement by having both a group mean change of amygdala activation with symmetric 1 SD intervals whose lower bound is less than an absolute precision criterion of (M-SD/2) \leq -0.35, and a positive group mean change of the amygdala-mPFC connectivity whose upper bound is greater than an absolute precision criteria of (M+SD/2) \geq 0.35. The criterion \pm 0.35 was selected as a value

clearly indicating more than "noise," as it places a substantial portion of the subjects in the improvement range, and thus is of potential clinical importance to warrant further study⁸².

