The methods to track enrollment described above will also aid in participant engagement and retention. Additional measures will nonetheless be taken to further increase retention. During screening, study staff will collect multiple forms of contact information (i.e. cell phone, email, mailing address, home phone) from each participant. This information will be stored in the encrypted database to be utilized for appointment reminders. Study staff will remind participants and confirm their appointment times through the participants' preferred method of contact. Study staff will also send reminder text messages (with the participants' permission) from a lab cell phone.

We will offer financial hs

for time taken to complete assessment visits and completing the study. Participants will be thanked for their time, following the study, and asked for feedback regarding feasibility and their experience completing the study.

Based on the above, and feasibility data from similar protocols by our group, we expect ≥80% retention rate through treatment and end of treatment assessments for Studies 1 and 2, and a ≥70% retention rate for the 6 month follow-up for Study 2. These numbers are consistent with Co-I [name]'s previously collected RCT on a behavioral insomnia intervention for suicide risk (NCT01958541) in a sample of N=77 high risk participants. In this study, which had more stringent inclusion criteria and a higher-risk sample, for which retention tends to be poor, feasibility data revealed discontinuation prior to treatment in only 9% of cases; retention was otherwise 100% through post-treatment phases. Attrition at follow-up was 3.8%, with no AE reported throughout the trial and excellent treatment adherence observed (>85% completed 75% of treatment sessions; >74% completed 100% of treatment sessions). The methods in NCT01958541 used to support retention and adherence will be adapted to the current project and aligned with in-use strategies to support the above strategy.

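### Section 9.1's 60% any-of-three hypothesis does not support its stated inference on the per-participant reading: with no treatment effect, well over 60% of scanned participants would be expected to meet it unless the three changes are very highly correlated.

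*Combined protocol and SAP*

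**What the plan says.** Protocol section 9.1 lists two statistical hypotheses. Hypothesis 2 is "At least 60% of participants show an increase in emotional regulation as indicated by any one of the three", the three being higher mPFC activation, higher mPFC-amygdala connectivity and lower amygdala activation than at baseline. The inference attached to it is "supporting that the targets can be modified in a majority of participants". The section gives no minimum change, task, contrast, denominator, no-effect rate or test.

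The Go rule differs. Section 3.1.1 requires that "at least 1 of 3 emotion regulation neuroimaging tasks must exhibit improvement by having both a group mean change of amygdala activation" and connectivity each reach a group-level bound. The synopsis (1.1) and section 2.1 state the same rule. Section 9.2 defines target engagement by the same two measures. Section 4.2.1 carries forward to the R33 phase only measures that meet the Go criteria.

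Section 9.3 plans both an intent-to-treat analysis with last observation carried forward and a completers analysis, and links neither to Hypothesis 2. The May 2025 SAP includes all available data, names two primary imaging measures, and neither uses nor withdraws the 60% rule.

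Two lesser differences sit nearby. Hypothesis 1 is "enroll 70 participants and retain ≥85% at 11 weeks", while the milestone in 3.1.1 is "enroll 70 participants and retain ≥80% at 11 weeks"; 1.1, 2.1 and 9.2 also use 80%, and 5.5.2 gives 80% or more as the expectation. Section 9.4.2 adds mPFC reactivity to the primary hypothesis; section 3.1.2, Table 1a and the SAP do not.

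**The concern.** A participant whose three measures only fluctuate between scans has three opportunities to move in the favourable direction, and any one of them is enough. With no effect, each opportunity is worth about one half, so the share of participants with at least one favourable sign starts well above 60%. A bar below the no-effect rate cannot show that the treatment modified anything.

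The study has a single arm, so no control group would reveal the chance rate. Hypothesis 2 could be reported as met, and quoted as prespecified support for target engagement, after a treatment that did nothing. It would also sit beside a Go rule that uses a different unit (group mean, not share of participants), a different set of measures (two, not three) and a different logic (both, not any one).

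**Working it through.** **Inputs.** From the documents: 70 enrolled and 56 retained (9.2), the 60% threshold and three indicators (9.1), and the two analysis populations (9.3). Assumed, because the documents give no values: one task; changes scored so that positive is favourable; trivariate normal with mean zero under no effect; a common correlation r, shown over a range.

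**The plan's own figures.** 0.80 × 70 = 56, as 9.2 states. 0.85 × 70 = 59.5, so 60 are needed for Hypothesis 1. Hypothesis 2 states no error rate or power, so there is no further figure to reproduce.

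**Step 1: no-effect share on the per-participant reading.** P(at least one favourable) = 1 − [1/8 + 3·asin(r)/(4π)]. At r = 0 this is 1 − 1/8 = 0.875. It falls to 0.60 only at r of about 0.91.

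**Step 2: chance of passing, completers.** 0.60 × 56 = 33.6, so 34 are needed: P(Binomial(56, p) ≥ 34).

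**Step 3: chance of passing, carried forward.** The schedule in 1.3 has imaging only at baseline and end of treatment, so a carried-forward dropout has zero change and is not an improver. 0.60 × 70 = 42 are needed from 56 scanned: P(Binomial(56, p) ≥ 42).

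**Step 4: slight harm.** If all three means worsen by 0.2 SD, P(at least one favourable) = 1 − P(Z1, Z2, Z3 all < 0.2) = 0.727, 0.672 and 0.574 at r = 0.3, 0.5 and 0.8. The binomial tails are then as in steps 2 and 3.

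| r | No-effect share | Pass, 34 of 56 | Pass, 42 of 70 (56 scanned) | Pass after 0.2 SD worsening, 34 of 56 | Same, 42 of 70 |
|---|---|---|---|---|---|
| 0 | 87.5% | >0.99 | 0.997 | not used | not used |
| 0.3 | 80.2% | >0.99 | 0.87 | 0.98 | 0.41 |
| 0.5 | 75.0% | 0.994 | 0.57 | 0.88 | 0.14 |
| 0.8 | 65.4% | 0.809 | 0.08 | 0.36 | 0.005 |

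On the 70 denominator the no-effect chance drops below one half at r of about 0.54. The reason is visible at r = 0.5: 56 × 0.75 = 42, exactly the number needed.

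**Step 5: the other reading.** If 60% must improve on one given indicator, P(Binomial(56, 0.5) ≥ 34) = 0.070. If any of the three indicators may reach 60%, the chance is 1 − (1 − 0.0704)³ = 0.197 when they are independent; simulation gives 0.20, 0.18, 0.18 and 0.15 at r = 0, 0.3, 0.5 and 0.8.

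**Step 6: tasks.** Section 9.1 names no task. If a favourable sign on any of the three tasks counted, there would be nine opportunities, and the no-effect share would be 1 − 0.5⁹ = 0.998 if they were independent. One task is therefore the lenient assumption.

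**The case against.** **The rule decides nothing.** Go/No-Go is set in 3.1.1, carry-forward follows it (4.2.1), and the SAP tests two measures with mixed models and contains no 60% rule. This stands. A reader might infer that a Go decision could rest on the 60% rule; the documents do not support that. The exposure is that the sentence remains in force under a heading of statistical hypotheses and could be cited.

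**Chance alone does not always pass it.** This also stands. A reader might infer from the completer figures that the rule passes by chance whatever the analysis population, or that it would probably pass even with slight worsening. Neither holds in general. Under the carried-forward population in 9.3, the no-effect chance is 0.57 at r = 0.5 and 0.08 at r = 0.8. After a 0.2 SD worsening it is at most 0.41 over r = 0.3 to 0.8, and even among completers it is 0.36 at r = 0.8. The SAP's reliance on available data favours the completer calculation, but nothing says that it replaces 9.3 for Hypothesis 2. The SAP's account of reduced amygdala reactivity through stronger top-down control also suggests positive correlation between at least two of the measures.

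**The wording allows a stricter reading.** It does, with a chance of 0.07, or about 0.15 to 0.20 over three indicators. The size of the problem depends on which reading is meant, and 9.1 does not say.

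**85% and 80% need not conflict.** A hypothesis can sit above a minimum milestone, and 3.1.1 cites earlier retention of 87% and 93%. A reader might call this a contradiction in the Go criterion; the documents do not show one. Retaining 56 to 59 meets the milestone and misses Hypothesis 1, and 9.1 attaches no consequence to that.

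**Conclusion.** The point holds on the per-participant reading. Among scanned participants, the expected no-effect share exceeds 60% for any common correlation below about 0.91, so reaching 60% does not support the claim that the targets were modified in a majority. The chance of a false pass is 0.81 to >0.99 with 56 completers over r = 0 to 0.8. On the carried-forward denominator of 70 with 56 scanned it runs from 0.997 down to 0.08, and passing by chance is the likelier outcome only up to r of about 0.54. These figures rest on symmetric normal no-effect changes, a common correlation that the documents do not give, and one task.

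Hypothesis 2 is also unreconciled with the two-measure group-mean Go rule and with the definition of engagement in 9.2. The harm is to interpretation, not to the Go decision. It should be fixed because the sentence is current text and the correction is cheap. The retention labels and the mPFC wording in 9.4.2 are secondary matters of consistency.

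**What to change.** In a dated SAP note or protocol amendment, state that the 60% any-of-three rule in 9.1 is not used and will not be cited as evidence of target engagement. Refer 9.1 to the definition in 3.1.1 and 9.2, which requires both amygdala reactivity and amygdala-mPFC connectivity. The May 2025 SAP already reports diagnostic checks on outcome data, so the note must be disclosed as made after data were examined.

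In the same note, as secondary edits:
- Label at least 80% (56 of 70) as the retention criterion and, if 85% (60 of 70) is kept, label it an expectation.
- Align 9.4.2 with 3.1.2, Table 1a and the SAP, so that mPFC reactivity is not part of the primary hypothesis.

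The cost is a short document, with no new data or analysis. The downside is that one stated hypothesis is no longer available as support for engagement.

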9.3 POPULATIONS FOR ANALYSES

We will conduct both an intent-to-treat (ITT) analysis using the last observation carried forward and analysis based on completers only, to assess bias caused by dropouts. Emotional distress assessments during the weekly treatment sessions will aid in understanding reasons for dropout.

9.4 STATISTICAL ANALYSES

9.4.1 GENERAL APPROACH

This project will employ robust statistical methods for each aim to rigorously test our model. We will maintain meticulous version control in the analysis utilizing git and will make our analysis and design code available via github to aid in transparency and methodological reproducibility.

9.4.2 ANALYSIS OF THE PRIMARY ENDPOINT(S)

Statistical Analyses: We hypothesize that in this single-arm study treatment with CBT-I will lead to improvements in Emotion Regulation Network function. Specifically, we predict that sleep restoration will be associated with greater increases in mPFC reactivity and mPFC-Amygdala Connectivity, and with decreases in Amygdala reactivity. An extended analysis of covariance (ANCOVA) will be used to test the primary hypothesis of change in Emotion Regulation Network function from baseline to end of treatment. We will characterize the association between our primary measures of Emotion Regulation Network function and that of our proximal outcome (sleep disruption as defined by sleep-EEG derived sleep efficiency) using a regression framework with age and sex included as covariates.

9.4.3 ANALYSIS OF THE SECONDARY ENDPOINT(S)

Statistical Analyses Related to Treatment Effects: We will examine the treatment effect on outcomes as measured by validated self-report questionnaires and sleep disruption measurements as well as the association of change in Emotion Regulation Network function with change in outcomes. We will also analyze within-

iREST Version 1.0
Protocol IRB-5 12-NOV-2020

subject trajectories of BDI and CSSRS scores, as well as sleep variables derived from actigraphy and daily sleep logs as a function of treatment dose, defined as cumulative number of CBT-I sessions.

Statistical Analyses Secondary Measures Related to Emotional Distress: Emotional distress secondary outcomes will be assessed using validated measures including Columbia Suicide Severity Rating Scale (CSSRS), World Health Organization quality of Life Assessment (WHOQoL-BRIEF), Patient Health Questionnaire (PHQ-9), and the Generalized Anxiety Disorder Scale (GAD-7). Secondary sleep disruption outcomes will include subjective experience of sleep disruption as indicated by the Insomnia Severity Index (ISI) and daily sleep logs, as well as sleep continuity and architecture variables derived from overnight sleep-EEG recording and actigraphy. Spectral analysis variables derived from the overnight sleep-EEG recording. We will also explore associations between emotion regulation related behaviors and physiology including behavior on the neuroimaging emotion regulation tasks (implicit threat priming, emotional conflict, and emotional response), measures of emotional reappraisal and suppression as assessed with the Emotion Regulation Questionnaire and the other domains, and Respiratory Sinus Arrhythmia (RSA). The statistical approach to analysis of the treatment effect on these outcomes will use ANCOVA, analogous to the analysis of target engagement (above).

Some measures will be collected daily (e.g. actigraphy and sleep logs) and weekly (BAI, BDI, CSSRS) over the course of treatment. Our general approach is to apply mixed linear models, using the daily/weekly reports to construct an individual specific estimate (functionally the mean and coefficient of variation of daily measurements for each naturalistic measure over a week) for baseline and follow-up, and then testing the effect of time (thus testing the within-person change over time). Random intercepts and slopes (and their covariance) at the person level will be included in our models. Random intercepts will be used to account for the clustering of observations within individuals across time; random slopes for key within-person predictors (e.g. 'time' or pre to post in this case) will be included to allow within-person slopes to be stronger for some individuals and weaker for others. In cases where random slopes are observed, we will test for potential subgroups/moderation (e.g., by age, sex, etc.; although we note that the small sample size somewhat limits our statistical power for such moderation tests).

Statistical Analyses Secondary Measures Related to Cohesive Factors of Dysfunction: Sparse unsupervised clustering and PCA analyses will be used to identify cohesive factors of dysfunction in a) targets of Emotion Regulation Network function, b) sleep disturbances, c) patterns of emotional distress, and d) behavioral measure of Emotion Regulation Network function at baseline. General linear models will be used to quantify the relationships within and between these factors.

